Statistical Methodology	Demographics data including race, sex, and age will be analyzed. Baseline characteristics of the cohort will be described. Results will be expressed as the mean and standard deviation.
Outcomes	Primary: Intraoperative, postoperative and daily cumulative opioid utilization Secondary: Methadone and metabolite enantiomers plasma AUC, maximum concentration, metabolite /methadone AUC ratios, metabolite formation clearance correlation of methadone enantiomer clearances and metabolite formation clearances, influence of CYP2B6*6 hetero or homozygote genotype

on above primary and secondary outcomes

1. Specific Aims.

- 1.1. To study the effects of a single dose of methadone on postoperative pain and opioid consumption in pediatric surgical patients.
- 1.2. Determine the pharmacokinetics of IV methadone (0.3-0.5 mg/kg) in children
- 1.3. Determine cytochrome P4502B6 (CYP2B6) genotype in patients receiving methadone, and any relationship to methadone clearance.
- 1.4. Determine from the primary caregiver the influence of the environment, social and psychological, on post-operative pain.

2. Background

Inadequate pain relief has a significant psychological impact upon children, including alterations in their perceptions of future painful experiences and medical procedures (1). The psychological ramifications of pediatric pain include posttraumatic stress disorder, lack of adherence to treatment, poor coping skills, changes in accuracy in the self-report of pain, and lack of trust in health-care providers (2). The degree to which this pain is controlled impacts the ability of patients to cope with the next pain episode. Patients undergoing major spine surgery experience severe pain in the postoperative period, which may increase morbidity and the incidence of complications, as well as prolong postoperative rehabilitation. Postoperative pain itself is a risk factor for development of chronic pain syndromes(3,4).

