6.3.1. Pain Assessment – Acute postoperative pain will be managed by St. Louis Children's Hospital pain services. Assessments are made in the postoperative period by a trained member of the research team blinded to intraoperative use of methadone. These will be conducted on each post-operative day until discharge or post op day 6, whichever comes first. Pain intensity is assessed using the Wong-Baker FACES scale employed by the inpatient nursing staff and previously validated (9). Pain relief is also assessed using a Colored-Visual Analog Scale. Other questions regarding pain relief and comfort may be given using a tablet. Sedation is assessed using a five-point scale (patient fully alert – not arousable). Itching and nausea are assessed using a five-point verbal scale (none, mild, moderate, severe or excruciating).

6.3.2. Pharmacokinetics – Pharmacokinetics studies will be performed for all patients in methadone treatment groups. Blood samples (approx 3 ml each) will be obtained before methadone and at approx 0.08, 0.5, 1, 1.5, 2, 3, 4, 6, 8, 10, 12, 24, 48, 72, and 96 hr after IV methadone administration. Blood samples will be drawn from the arterial line for the first 24 hours and then from the venous lines or collected with routine labs. Total amount of blood drawn will be approx. 48 mls for pharmacokinetic testing for up to four days. Blood will only be collected while the patient is hospitalized; if the patient is discharged from the hospital no further collections will be made.

6.3.3. CYP Genotyping – For all patients, 5 ml of blood will be drawn for CYP2B6 genotyping. Genotyping will be performed at the WUSTL Genome Technology Access Center (GTAC).

6.3.4. Urine samples- For all patients, 24 hour- urine collections will be conducted for up to 96 hours after surgery.

6.4. *Postoperative Period*

Patients receive standard of care analgesia using patient control analgesia method, primarily with hydromorphone or morphine as determined by the treating physician. Postoperative

care is not altered for purposes of this study.

7. Data Collection and Monitoring.

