9.2.4. Maximum plasma EDDP concentration

9.2.5. AUC (plasma EDDP)/AUC (plasma methadone)

9.2.6. Cmax (plasma EDDP)/Cmax (plasma methadone)

9.2.7. Urine concentration of methadone and EDDP

9.2.8. Side effects of opioids

9.3. Analysis.

9.3.1. Sample Size- we decided to use our pilot study data which looked into the pharmacokinetics of methadone in pediatric surgical patients attending St. Louis Children Hospital. This is actually the pooling place for the present study and therefore the information provided is a "true" sample of the data to be collected. The pilot study revealed that patients undergoing spinal fusion surgery used an average of 274 mg of morphine equivalents within 72 hours post-surgery with a standard deviation of 82 mg. Based on this information and assuming a 2-sided test of two independent sample means with α 0.05, we were able to estimate that the proposed study will have at least 80% power to detect 30% decrease in the total postoperative consumption of morphine or morphine equivalents among the patients assigned to the two treatment groups combined when compared to the control group

patients. Specifically, with a total sample of approx. 60 patients assigned equally across study groups (1:2 randomization), we will have adequate statistical power to detect a clinically meaningful reduction of opioid use in patients receiving a single dose of methadone before incision.

To study the effect size between two groups, power calculations were made with alternative mean differences in morphine consumption over 72 hours post-surgery with assumed variation range and a 2-sided test with $\alpha = 0.05$. Based on our conservative assumptions, we found that, with a sample as small as 20 in each group, we will have 80% power to detect a minimum difference between 10 and 20 mg of morphine use, depending on the observed variability between the two groups.

9.3.2. Statistical Analysis- Baseline characteristics of the cohort will be described. Demographics data including race, sex, and age at study entry will be analyzed using chi-square and t- test appropriate. Total daily opioid consumption and pain scores using both Wong-Baker FACES and colored visual analogue scale, will be compared between the groups. Outcome measures will be expressed by the mean and standard deviation. Group outcomes will be compared across the two or three groups, using t-test and/or analysis of variance, ANOVA and MANCOVA to account for potential cofounders.

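### Mean and SD for the five-grade sedation, itching and nausea scores will not show how many patients in each arm had a severe grade

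*Combined protocol and SAP*

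**What the plan says.** Three items are scored on ordered grades on each postoperative day, up to discharge or day 6 (6.3.1).

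- Sedation: "Sedation is assessed using a five-point scale", with only the two ends described, from fully alert to not arousable.
- Itching and nausea: "Itching and nausea are assessed using a five-point verbal scale (none, mild, moderate, severe or excruciating".

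The list of secondary assessments includes "9.2.8. Side effects of opioids".

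Section 9.3.2 names these outcomes for comparison: "Total daily opioid consumption and pain scores using both Wong-Baker FACES and colored visual analogue scale, will be compared between the groups". It then gives a general rule, "Outcome measures will be expressed by the mean and standard deviation", and says that group outcomes will be compared "using t-test and/or analysis of variance, ANOVA and MANCOVA to account for potential cofounders". The Statistical Methodology row of the synopsis has a similar line: "Results will be expressed as the mean and standard deviation". The only categorical method, chi-square, is in the sentence on demographics. Pharmacokinetic outcomes have their own section, 9.3.3.

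No section plans counts per grade, a worst grade per patient, a proportion at severe grades, an ordinal or rank method, or a way to combine the repeated daily scores.

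**The concern.** The steps between ordered grades have no fixed size, and for tolerability the upper end matters most. A mean lets a few high grades in one arm be offset by more low grades in the same arm. An SD may widen, but it does not say how many patients had a severe grade.

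This matters here because 10.1 names sedation as the most common effect of opioids such as methadone and nausea or vomiting as its most common adverse effect. The abstract says the trial studies 0.3–0.5 mg/kg, against 0.1–0.3 mg/kg in the group's earlier work. A reader will want to see tolerability by arm and dose, and the planned summary does not give it.

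**Working it through.** **1. What the plan's own figures cover.** No figure is given for side effects. The power statement in 9.3.1 concerns morphine equivalents only: mean 274 mg, SD 82 mg, 30% decrease, two-sided α 0.05, about 60 patients at 1:2. It holds as a lower bound:

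- difference = 0.30 × 274 = 82.2 mg
- standard error = 82 × √(1/20 + 1/40) = 22.46 mg
- power = Φ(82.2/22.46 − 1.96) = Φ(1.70) ≈ 95.5% (94.9% with the t distribution)

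From this I take only the arm sizes, 20 control and 40 methadone.

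**2. Can equal means coexist with different severe counts?** The distributions below are assumptions. Grades are scored 0–4, one score per patient, so nothing depends on averaging over days.

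| Case | Arm | Patients at grade 0/1/2/3/4 | Mean | SD | Top two grades |
|---|---|---|---|---|---|
| Both | Control | 6/8/6/0/0 | 1.00 | 0.79 | 0/20 |
| A | Methadone | 18/12/4/4/2 | 1.00 | 1.20 | 6/40 |
| B (milder) | Methadone | 16/12/8/3/1 | 1.02 | 1.07 | 4/40 |

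- Control mean = (8×1 + 6×2)/20 = 1.00
- Case A mean = (12×1 + 4×2 + 4×3 + 2×4)/40 = 40/40 = 1.00
- Case B mean = (12×1 + 8×2 + 3×3 + 1×4)/40 = 41/40 = 1.025
- t-test against control: p = 1.00 (A) and p = 0.93 (B)

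**3. The same data as counts, with Clopper–Pearson intervals.**

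- Control: 0/20, 95% CI 0% to 16.8% (upper limit 1 − 0.025^(1/20))
- Case A: 6/40 = 15%, 95% CI 5.7% to 29.8%
- Case B: 4/40 = 10%, 95% CI 2.8% to 23.7%

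**4. Is a handful of severe grades plausible?** If the true rate on methadone were 5%, the chance of at least one such patient among 40 is 1 − 0.95^40 = 87%. At 10% it is 1 − 0.90^40 = 99%. Both rates are assumptions.

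**5. Does a different test help?** Not at this size. In case A, Mann–Whitney gives p = 0.53 and Fisher's exact test p = 0.165. In case B they give 0.80 and 0.29. Fisher power at 20 v 40 is about 10% for true rates of 5% v 15%, and 26% for 5% v 20%.

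**The case against.** The strongest reply is that 9.3.2 never names side effects. It names opioid consumption and pain scores, and the mean-and-SD sentence follows directly. This is correct: the rule reaches sedation, itching and nausea only through general wording. On the narrower reading, though, a listed secondary assessment has no analysis at all, and the same addition is needed.

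Three stronger readings are tempting, and the documents do not support them.

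- **The plan averages grades over patients and six days.** No section says so. The choice matters. Suppose that 3 of 40 methadone patients and no controls reach the top sedation grade on day 1 only. On a 1–5 scale, a six-day mean then moves by 4 × (3/40)/6 = 0.05. Summarised by day, with 30% of other readings one grade up (an assumption), the day-1 shift is (3/40) × (5 − 1.3) = 0.28, with SDs of about 1.08 v 0.46. That would not look flat.
- **Dangerous events would go unseen.** An independent colleague reviews serious and unexpected adverse events (8.1), a serious event resulting from methadone suspends the study (8.4), and 10.1 defines respiratory depression separately. These routes work patient by patient. None compares side-effect grades between arms, the documents do not link any sedation grade to serious-event reporting, and severe itching or nausea need not be a serious event.
- **The t-test is what fails, and a rank test would succeed.** In simulations of that three-patient scenario, the t-test on patient means and the Wilcoxon test on worst grade both reject about 6% to 7% of the time. With four patients, both reject about 8% to 9%. Fisher's test for 3/40 v 0/20 gives p = 0.54. The limit is sample size.

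It is also fair to say that means of five-point ratings are common, that these are secondary items in a 60-patient trial, and that the SD does widen in the examples. This lowers the weight of the point but does not remove it.

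**Conclusion.** The point holds as a reporting gap. Under the only rule that can reach these outcomes, the results would not show how many patients in each arm had a severe grade. Equal means of 1.00 can coexist with 6/40 v 0/20 in the top two grades.

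That example shows what can happen and is not a forecast. It rests on assumed distributions, on arm sizes of 20 and 40, and on taking the top two of five grades as severe. That a mean can conceal a severe tail does not depend on those exact values. The intervals overlap, so counts would not establish a difference between arms either, but they would put the data in front of the reader. The change is worth making; it does not affect the primary analysis.

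**What to change.** Add to 9.3.2, for sedation, itching and nausea:

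- Take each patient's worst grade, overall and in the first 24 hours, and state when that period starts.
- Tabulate the number and percentage of patients at each grade, by arm and by methadone dose.
- Give exact (Clopper–Pearson) 95% CIs for the proportion at the severe grades. Fix the cut-off in advance; this matters most for sedation, where 6.3.1 describes only the two ends of the scale.
- Make these tables the main summary in place of mean and SD.
- Show the number of days assessed beside the overall worst grade, because assessment stops at discharge or day 6 and patients may be observed for different lengths of time.

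An ordinal or rank comparison may be added as support, but it brings no meaningful power at 20 v 40 and should not be the headline.

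The cost is a few sentences in the plan and a few extra tables with wide intervals. The daily grades are already collected, so no visits, patients or measurements are added.

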Evaluating the role of methadone in pediatric spinal surgery patients is advantageous because 1) high dose of opioids are routinely used during and after the surgery, 2) methadone is one of the commonly used opioids for this surgery, 3) an arterial catheter or a second IV catheter is needed for the surgery and can be used to draw blood samples, 4) prolonged analgesia from methadone is expected to decrease the need for additional opioids.

Assessment of pain has become standard practice in the treatment of pediatric patients. Several pain scales including the Wong-Baker FACES scale, the Oucher Scale and the Visual Analog Scale (VAS) have been USED in children who were experiencing pain (14,15).

In this study, we propose to evaluate postoperative opioid consumption, pain intensity and pain relief in pediatric patients undergoing posterior spinal fusion who will receive a single dose of methadone during surgery. In addition, we will study dose effect of ing various doses of methadone, between 0.3 – 0.5mg/kg IBW. Secondarily, we will determine the pharmacokinetics of higher doses of IV methadone in children who are undergoing anesthesia and surgery. Lastly, we will determine the role of CYP2B6 genotype on methadone pharmacokinetics.

3. Drug Information

Methadone hydrochloride is a synthetic μ -agonist with multiple actions qualitatively similar to those of morphine. Onset of effect is about 2-10 min for parenteral dosing. Methadone is primarily metabolized by N-demethylation to an inactive metabolite, 2-ethylidene-1,5-dimethyl-3,3-diphenylpyrrolidene (EDDP). In vitro, cytochrome P450 enzymes, primarily CYP3A4 and CYP2B6 are responsible for conversion of methadone to EDDP and other inactive metabolites. In vivo, CYP2B6 is a major determinant of metabolism to inactive metabolites which are excreted mainly in the urine. The terminal half-life ($T_{1/2}$) in healthy children averages 24-36 hrs. Like adults, in teenage children, most common side effect of methadone, like other opioids, is sedation, nausea and vomiting. Respiratory depression is the chief hazard associated with methadone, like all opioids. QT prolongation and serious arrhythmia have been observed during treatment with methadone and have been associated with doses

>200 mg/day(16).

4. Eligibility

4.1. Inclusion Criteria.

- 4.1.1. Age 11-18 years
- 4.1.2. Undergoing general anesthesia and idiopathic posterior spinal surgery with anticipated postop inpatient stay of > 3 days

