6.1. Preoperative and Intraoperative Period

Parents and patients will be asked to complete a questionnaire prior to the child's surgery. This will take approximately 5 minutes. Participants can choose to complete the survey and not participate in the randomized part of the study. The questionnaire is to determine if factors such as anxiety and social economic attributes interact with each other prior to surgery. If only participating in the questionnaire information regarding demographic data, pain scores and pain treatment will be collected from the patients' medical record.

Patients will receive standard physiologic monitoring for anesthesia and postoperative care. Using a modified Dixon up and down dose finding method, subjects in the first cohort are randomized 1:2 to receive either control (standard intraop opioid) or methadone HCl (0.4 mg/kg ideal body weight, IBW). In the second cohort, subjects are randomized 1:2 to receive either control (standard intraop opioid) or methadone HCl (0.3 mg/kg ideal body weight, IBW).

Anesthesia and surgical care will not be altered for the purposes of this investigation, except that subjects in groups I and II, will receive methadone as their intraoperative opioid, rather than leaving the choice of intraoperative opioid to the anesthesiologist (patients typically may get methadone or any other opioid). The control group patients will receive intraoperative analgesia with opioids other than methadone left at the discretion of their anesthesiologist. Additional

randomized cohorts may be included to study IV methadone HCl doses within the range of 0.3 – 0.5mg/kg IBW, based on interim study findings and analysis.

6.2. *Administration of Study Medication.*

Methadone is administered as an IV bolus after induction of anesthesia and after an arterial line is placed. Methadone hydrochloride is available commercially as a solution for injection of 10 mg/ml. Based on our experience, we believe that additional postoperative opioids will still be needed, but that increasing methadone doses will result in lessened postoperative opioid use.

6.3. *Assessments.*

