- 7.1. *Assessment of Pain Intensity and Pain Relief*- Each pediatric patient enrolled in the study, regardless of type of opioid received, will have pain intensity assessed each post operative hospital day (HD) for up to six days or until discharge, whichever comes first. The Wong-Baker FACES scale and Verbal analogue scale, available as laminated cards, are currently used by the nursing staff to assess pain on the inpatient units. Pain will also be assessed by patients using a colored-visual analogue scale. The study personnel performing the assessment will have a set script to read when administering the scale.
- 7.2. *Opioid Consumption*. The inpatient medical record will be used to calculate the amount of morphine or morphine equivalents administered for each 24-hour period that subjects are receiving opioid analgesics. Oral opioid administration will be totaled through discharge for each 24-hour period as well.
- 7.3. *Other Required Studies*. Required baseline measurements that will be obtained from the EMR are vital signs, weight, height, and peripheral oxygen saturation by pulse oximetry and are all collected as standard of care.
- 7.4. *Drug and metabolite concentrations and drug effects*. Plasma concentrations of methadone and the mono N-demethylated metabolite EDDP will be determined by HPLC-mass spectrometry.
- 7.5. *Sources of Research Material*. Background information including demographic data, outpatient medications used, and chronic medical conditions will be obtained from the medical record at the time of enrollment

8. Data and Safety Monitoring Plan.

In general, the PI has developed a specific set of Standard Operating Procedures (SOPs) for clinical research. All individuals working under the PI are required to read and be totally familiar with and compliant with the SOPs. The PI's SOPs are in part developed from and are compliant with the Institutional guidelines, including those for a) Interactions with the Washington University Human Subjects Review Committee, b) Informed Consent Development and Implementation, c) Subject Recruitment and Screening, d) Subject Management While on Study, e) Adverse Event Reporting.

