9.1. Primary Assessment

9.1.1. Overall morphine (equivalents) consumption for each patient during hospitalization

9.1.2. Absolute pain scores and pain relief scores

9.2. Secondary Assessments

9.2.1. Methadone clearance

9.2.2. Maximum plasma methadone concentration

9.2.3. Area under the curve (AUC) of plasma EDDP vs time

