9.3.3. Methadone Calculations -Methadone and EDDP plasma concentration-time data will be analyzed by linear and nonlinear regression analysis using noncompartmental or compartment models to determine total area-under-the-curve (AUC), and systemic clearance. Results will also be analyzed using population methods, with age and dose as covariates, to determine linearity of pharmacokinetic parameters and effects of age.

10. Risk Assessment

10.1. *Methadone* The most common clinical effect of opioids such as methadone is mild sedation. Based on prior experience with this opioid and doses, and prior published experience, some subjects might experience mild sedation for about 0.5-1 hr after methadone administration, were they awake. Since patients will be anesthetized during this period, clinical methadone effects are expected to be no different from those of anesthesia and any other opioid administered during anesthesia. We have further attempted to minimize the risk to the patients by following a conservative approach of two step randomization. The most common adverse effect of methadone is nausea and/or vomiting. Patients will have only clear liquids 6 hours before anesthesia, per standard of care. If nausea and/or vomiting occur, they will be treated using the standard of care for all post-anesthesia nausea and vomiting. Respiratory depression is a potential concern with all opioids, but has not been problematic at the doses of methadone that

have been used in similar previous studies. Mild respiratory depression is defined as respiratory rate <8/min in adults and children older than 10, <12–16 in children age 3-10, and <20 in children younger than two. Severe depression will be defined as the administration of naloxone to a patient with respiratory rate < 6/min. If treatment is required, naloxone will be used. Patients in the hospital are routinely periodically monitored by blood pressure and/or pulse oximetry, and receive supplemental oxygen if dictated, according to good clinical practice.

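### Section 9.3.3 sets out to estimate the effect of age in 11-18-year-olds without a body-size term, clearance scale or dose unit, so on absolute clearance the age coefficient would carry growth (secondary PK analysis, low severity).

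*Combined protocol and SAP*

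**What the plan says.** - Section 9.3.3 first derives parameters by "noncompartmental or compartment models to determine total area-under-the-curve (AUC), and systemic clearance". It then adds the population step: "Results will also be analyzed using population methods, with age and dose as covariates, to determine linearity of pharmacokinetic parameters and effects of age". No body-size covariate, clearance scale or dose unit is given.
- Section 9.2.1 lists "Methadone clearance" as a secondary assessment, also without a scale.
- Section 4.1.1 enrols "Age 11-18 years".
- Section 7.3 provides the size data: "Required baseline measurements that will be obtained from the EMR are vital signs, weight, height". No section links them to the PK model.
- Section 6.1 states the administered dose per kg of IBW, for example "methadone HCl (0.4 mg/kg ideal body weight, IBW". Section 9.3.3 does not carry that unit into the model.

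**The concern.** Estimating an effect of age is one of the two purposes given for the population model. Over this age range older patients are, on average, larger, and clearance in volume per time would be expected to rise with size. If the model holds only age and dose, the age term takes up whatever growth effect the clearance scale has not removed. A mg/kg dose covariate cannot help, because it takes only the few assigned values and carries no information on size. A mg dose carries some, but only through IBW. The dose coefficient then picks up size as well, which disturbs the model's other purpose, linearity. The trial could therefore report an age effect on methadone kinetics that is only a size effect, with a magnitude and sign set by choices the plan leaves open.

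**Working it through.** The plan gives no sample size, precision or expected value for this analysis, so there is no figure of its own to reproduce.

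**Inputs from the documents.** Ages 11-18 (4.1.1). 60 evaluable patients at 2:1 (synopsis), so 60 x 2/3 = 40 on methadone, all with PK sampling (6.3.2). Dose levels 0.4 and 0.3 mg/kg IBW (6.1).

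**Assumptions, not in the documents.** Mean weight 40 kg at 11 and 65 kg at 18; no true age effect; clearance proportional to weight^b with b = 0.75 or 1; half the methadone patients at each dose; age tested at a nominal 5%.

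**Closed form.** Let R = 65/40 = 1.625 be the weight ratio, 18 versus 11 years.
- Absolute clearance, apparent age ratio R^b: 1.625^0.75 = 1.44 (+44%); b = 1 gives 1.625 (+63%).
- Clearance per kg, R^(b-1): 1.625^-0.25 = 0.886 (-11%); b = 1 gives 1.00.
- Other weight ranges at b = 0.75: 35-60 kg gives 1.50 absolute and 0.874 per kg; 40-70 kg gives 1.52 and 0.869.
- Exponent fixed at 0.75 when the truth is 1: 1.625^0.25 = 1.13 (+13%).

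**Simulation.** Log clearance = b x log(weight) + error, regressed on age and log dose by ordinary least squares (a simplification of a mixed model). There were 27 scenarios: three age distributions, weight CV at a given age 15, 20 or 30%, and clearance CV 25, 40 or 60%. IBW CV at a given age was 10%. The share of a patient's IBW deviation passing into total weight was 0, 0.5 or 1. That makes 27 x 3 x 2 exponents = 162 cells of 6,000 runs. Entries are the apparent change in clearance from 11 to 18, with the share of runs in which the age test rejects.

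| Model | True exponent 0.75 | True exponent 1 |
|---|---|---|
| Absolute, dose in mg/kg | +42% to +45% (11-64%) | +58% to +64% (14-82%) |
| Absolute, dose in mg | +26% to +45% (8-45%) | +36% to +64% (8-62%) |
| Per kg or per kg IBW | -10% to -12% (5-14%) | about 0 (4-6%) |
| Weight effect estimated | -1% to +1% (4-6%) | about 0 (4-6%) |

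The spread in the second row comes mainly from how closely IBW tracks total weight. In a separate run with weight ratios of 1.2 to 1.75 and b = 0.75, a mg dose on absolute clearance also gave an average dose coefficient of 0.18-0.21 although the simulated kinetics were linear.

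**Which size metric.** The table generates clearance from total weight. If clearance follows IBW instead (clearance CV 40%, weight CV 15-30%), an estimated total-weight term is no longer safe. Total weight is then a noisy proxy, its coefficient is attenuated, and age takes up the rest: +21% to +45% (9-32%) at b = 0.75 and +31% to +66% (15-45%) at b = 1. A fixed exponent of 0.75 on either metric leaves 0 to +1% if the truth is 0.75, and +12% to +13% if it is 1 (clearance CV 40%). This robustness depends on total weight and IBW having the same mean trend with age, as assumed here.

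**The case against.** The strongest reply has four parts.

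- **The covariate list is not closed.** Section 9.3.3 does not say that age and dose are the only covariates. Aim 1.3 relates CYP2B6 genotype to clearance, yet 9.3.3 does not list genotype either. This stands: a reader might infer that the plan rules out a size term, and the text does not support that. It remains true that the one model described has none and that nothing points the analyst to the weight and height collected.
- **The protocol's own unit points to a small effect.** Dosing is per kg IBW, and clearance on the same scale gives about -11% or nothing, with a rejection rate of at most 14%. This stands as the more natural reading. It is still an inference, because the administration unit is not stated as the scale of clearance or of the dose covariate.
- **The large figures are conditional and rest on assumed inputs.** A reader might infer from the absolute-clearance rows that the reported age effect will be badly wrong. The documents do not support that: no section says clearance will be absolute, and the weights, variabilities and exponents are mine.
- **Adding total weight with an estimated exponent is not a safe remedy.** This stands, as shown above, and it changes the recommendation. It does not count against scaling for size with a fixed exponent.

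**Conclusion.** The point holds as a gap in the analysis specification. Run as listed on absolute clearance, the model would attribute growth to age: about +26% to +45% from 11 to 18 at exponent 0.75. On per-kg or per-kg-IBW clearance the effect is about -11% at exponent 0.75 and nil at exponent 1. These figures rest on mean weights of 40 to 65 kg, no true age effect and 40 methadone patients.

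The reach is limited. A reader might take the age effect to be a study objective, but it is not among Specific Aims 1.1-1.4, the synopsis outcomes or assessments 9.2.1-9.2.8. It appears only as a stated purpose of the population model in 9.3.3. The randomised opioid comparison is unaffected and no trial decision depends on the age coefficient. Severity is low, but the correction is cheap and worth making.

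**What to change.** In 9.3.3:

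1. State the scale on which clearance is analysed and reported, and whether dose enters in mg or mg/kg.
2. Scale clearance and volume for body size in the base model, before assessing age and dose. Pre-specify the size metric (total weight or IBW, both obtainable from the weight and height already collected) and a fixed allometric exponent. If IBW is used, name the formula, since the documents give none.
3. Report as sensitivity analyses the other size metric, and either an exponent of 1 (per-kg clearance) or an estimated exponent.

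**Cost.** A little more analysis and no new data. Against the unscaled model, fixing the exponent at 0.75 costs at most about 10% in the precision of the age coefficient. If the true exponent is 1, a residual age effect of about +11% to +14% remains (5-14% rejection), which the sensitivity analyses would help to reveal. An estimated exponent avoids that if the size metric is right. It widens the standard error of the age coefficient by up to about 39% against the per-kg model on total weight, and by more on IBW, and it is biased if the metric is wrong. That is why it belongs in the sensitivity analyses.
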